12.8 Trial restrictions

Women of childbearing potential will be required to use highly effective contraception for the duration of the trial and for 7 days after the completion of the last scan. This includes:

- Intrauterine Device (IUD)
- Oral contraceptive (progestogen alone note combined oral contraceptives containing oestrogen and progesterone are not permitted). Progesterone-only hormonal contraception preparations are only considered acceptable if the main mechanism of action is inhibition of ovulation.
- True abstinence (where this is in accordance with the participants preferred and usual lifestyle)

Men will be required to use adequate contraception for the entire duration of the trial and for 7 days after completion of the last scan.

- Barrier contraception (condom and occlusive cap e.g. diaphragm or cervical cap with spermicide)
- True abstinence (where this is in accordance with the participants preferred and usual lifestyle)

13 Assessment of Safety

13.1 Definitions

13.1.1 Adverse event (AE)

Any untoward medical occurrence in a participant or clinical trial participant administered a medicinal product and which does not necessarily have a causal relationship with this treatment.

An adverse event can therefore be any unfavourable and unintended sign (including an abnormal laboratory finding), symptom, or disease temporally associated with the use of an investigational medicinal product, whether or not considered related to the investigational medicinal product.

Please note: Recording of all adverse events must start from the point of Informed Consent regardless of whether a participant has yet received a medicinal product.

13.1.2 Adverse reaction to an investigational medicinal product (AR)

All untoward and unintended responses to an investigational medicinal product related to any dose administered. All adverse events judged by either the reporting investigator or the sponsor as having a reasonable causal relationship to a medicinal product qualify as adverse reactions. The expression reasonable causal relationship means to convey in general that there is evidence or argument to suggest a causal relationship.

13.1.3 Unexpected adverse reaction

An adverse reaction, the nature, or severity of which is not consistent with the applicable reference safety information (RSI) (e.g. investigator's brochure for an unapproved investigational product or summary of product characteristics (SmPC) for an authorised product). When the outcome of the adverse reaction is not consistent with the applicable RSI this adverse reaction should be considered as unexpected.

The term "severe" is often used to describe the intensity (severity) of a specific event. This is not the same as "serious," which is based on participant /event outcome or action criteria.

13.1.4 Serious adverse event or serious adverse reaction (SAE / SAR)

Any untoward medical occurrence that at any dose:

- results in death
- is life-threatening
- requires hospitalisation or prolongation of existing inpatients' hospitalisation
- results in persistent or significant disability or incapacity
- is a congenital anomaly or birth defect.
- is an important medical event Some medical events may jeopardise the participant or may require an intervention to prevent one of the above characteristics/ consequences. Such events (hereinafter referred to as 'important medical events') should also be considered as 'serious'

Life-threatening in the definition of a serious adverse event or serious adverse reaction refers to an event in which the participant was at risk of death at the time of event; it does not refer to an event which hypothetically might have caused death if it were more severe.

13.1.5 Suspected Unexpected Serious Adverse Reaction (SUSAR)

A serious adverse reaction, the nature and severity of which is not consistent with the information set out in the Reference Safety Information.

13.1.6 Reference Safety Information (RSI)

A list of medical events that defines which reactions are expected for the IMP within a given trial and thus determining which Serious Adverse Reactions (SARs) require expedited reporting.

For this trial the Reference Safety Information is: located in the most recent version of the Investigator's Brochure for the PET Radiopharmaceutical [¹⁸F]CETO approved by the MHRA for use in this trial.

Due to the absence of any previous human data for [¹⁸F]CETO, all events will be considered unexpected. Therefore, all SARs in the trial will meet the unexpected criteria and will be reported as SUSARs.

13.2 Expected Adverse Reactions/Serious Adverse Reactions (AR /SARs)

All expected Adverse Reactions are listed in the latest MHRA approved version of the RSI as specified in section 12.1.6. This will be used when making a determination as to the expectedness of the adverse reaction. If the adverse reaction meets the criteria for seriousness, this will be reported as per section 12.5

13.3 Expected Adverse Events/Serious Adverse Events (AE/SAE)

We are not aware of any adverse effects associated with [18F]CETO from previous studies.

Before the PET/CT scan, a cannula will be sited, and this will be used for injecting the tracer. There may be local bruising following insertion of the cannula. Localised bruising associated with cannula insertion will not be recorded as an AE.

13.4 Evaluation of adverse events

The Sponsor expects that adverse events will be recorded from the point of Informed Consent regardless of whether a participant has yet received a medicinal product. Individual adverse events will be evaluated by the investigator. This includes the evaluation of its seriousness, and any relationship between the investigational medicinal product(s) and/or concomitant therapy and the adverse event (causality).

13.4.1 Assessment of seriousness

Seriousness will be assessed against the criteria in section 12.1.4. This defines whether the event is an adverse event, serious adverse event or a serious adverse reaction

13.4.2 Assessment of causality

Definitely: A causal relationship is clinically/biologically certain. This is therefore an Adverse Reaction

Probable: A causal relationship is clinically / biologically highly plausible and there is a plausible time sequence between onset of the AE and administration of the investigational medicinal product and there is a reasonable response on withdrawal. **This is therefore an Adverse Reaction.**

Possible: A causal relationship is clinically / biologically plausible and there is a plausible time sequence between onset of the AE and administration of the investigational medicinal product. **This is therefore an Adverse Reaction.**

Unlikely: A causal relation is improbable and another documented cause of the AE is

most plausible. This is therefore an Adverse Event.

Unrelated: A causal relationship can be definitely excluded and another documented cause of the AE is most plausible. **This is therefore an Adverse Event.**

Unlikely and Unrelated causalities are considered NOT to be trial drug related Definitely, Probable and Possible causalities are considered to be trial drug related

A pre-existing condition will not be recorded as an AE or reported as an SAE unless the condition worsens during the trial and meets the criteria for reporting or recording in the appropriate section of the CRF.

13.4.3 Clinical assessment of severity

Mild: The participant is aware of the event or symptom, but the event or symptom

is easily tolerated

Moderate: The participant experiences sufficient discomfort to interfere with or reduce

his or her usual level of activity

Severe: Significant impairment of functioning; the subject is unable to carry out usual

activities and / or the participant's life is at risk from the event.

13.4.4 Recording of adverse events

Adverse events and adverse reactions will be recorded in the medical notes and the appropriate section of the CRF and/or AE/AR log. Serious Adverse Events and Serious Adverse Reactions will be reported to the sponsor as detailed in section 12.5.

13.5 Reporting serious adverse events

Each Principal Investigator will record all adverse events and report serious adverse events to the Chief Investigator and Sponsor using the trial specific SAE form within 24 hours of their awareness of the event.

The Principal Investigator will be responsible for ensuring the assessment of all SAEs for expectedness and relatedness is completed and the onward notification of all SAEs to the Sponsor immediately but not more than 24 hours of first notification. The sponsor will keep detailed records of all SAEs reported to them by the trial team.

The Chief Investigator will be responsible for prompt reporting of all serious adverse event findings to the competent authority (e.g. MHRA) of each concerned Member State if they could:

- adversely affect the health of participants
- impact on the conduct of the trial
- alter the risk to benefit ratio of the trial
- alter the competent authority's authorisation to continue the trial in accordance with Directive 2001/20/EC

The completed SAE form must be emailed to the CTC. Details of where to report the SAE's can be found on the SAE form and the front cover of the protocol.

13.6 Reporting of Suspected Unexpected Serious Adverse Reactions (SUSARs)

All suspected adverse reactions related to an investigational medicinal product (the

tested IMP and comparators) which occur in the concerned trial, and that are both unexpected and serious (SUSARs) are subject to expedited reporting. Please see section 12.1.6 for the Reference Safety Information to be used in this trial.

13.6.1 Who should report and whom to report to?

The Sponsor will delegate the responsibility of notification of SUSARs to the Chief Investigator. The Chief Investigator must report all the relevant safety information previously described, to the:

- Sponsor
- competent authorities in the concerned member states (eg MHRA)
- Ethics Committee in the concerned member states

The Chief Investigator shall inform all investigators concerned of relevant information about SUSARs that could adversely affect the safety of participants.

13.6.2 When to report?

13.6.2.1 Fatal or life-threatening SUSARs

All parties listed in 12.6.1 will be notified as soon as possible but no later than **7** calendar days after the trial team and Sponsor has first knowledge of the minimum criteria for expedited reporting.

In each case relevant follow-up information will be sought and a report completed as soon as possible. It will be communicated to all parties within an additional **8 calendar days**.

13.6.2.2 Non-fatal and non-life-threatening SUSARs

All other SUSARs and safety issues will be reported to all parties listed in 12.6.1 as soon as possible but no later than **15 calendar days** after first knowledge of the minimum criteria for expedited reporting. Further relevant follow-up information will be given as soon as possible.

13.6.3 How to report?

13.6.3.1 Minimum criteria for initial expedited reporting of SUSARs

Information on the final description and evaluation of an adverse reaction report may not be available within the required time frames for reporting. For regulatory purposes, initial expedited reports will be submitted within the time limits as soon as the minimum following criteria are met:

- a) a suspected investigational medicinal product
- b) an identifiable participant (e.g. trial participant code number)
- c) an adverse event assessed as serious and unexpected, and for which there is a reasonable suspected causal relationship
- d) an identifiable reporting source

and, when available and applicable:

- a unique clinical trial identification (EudraCT number or in case of non-European Community trials the sponsor's trial protocol code number)
- a unique case identification (i.e. sponsor's case identification number)

13.6.3.2 Follow-up reports of SUSARs

In case of incomplete information at the time of initial reporting, all the appropriate information for an adequate analysis of causality will be actively sought from the reporter or other available sources. Further available relevant information should be reported as follow-up reports.

In certain cases, it may be appropriate to conduct follow-up of the long-term outcome of a particular reaction.

13.6.3.3 Format of the SUSARs reports

Electronic reporting is the expected method for expedited reporting of SUSARs to the competent authority. The format and content as defined by the competent authority will be adhered to.

13.7 Pregnancy Reporting

Pregnancies within the trial will be reported to the Chief Investigator and the Sponsor using the relevant Pregnancy Reporting Form within 24 hours of notification. Participants will be advised to notify the trial team where they become aware of a pregnancy following the conclusion of their participation in the trial as follows:

- Pregnant participants: conception occurring within 1 month of the last IMP dose
- Pregnant partners of male participants: conception occurring between the date of the first IMP dose and 7 days following the last IMP dose

Pregnancy is not considered an AE unless a negative or consequential outcome is recorded for the mother or child/fetus. If the outcome meets the serious criteria, this would be considered an SAE.

14 Toxicity – Emergency Procedures

Administration of [¹⁸F]CETO will take place in a NHS PET-CT unit which is fully equipped to deal with any adverse reaction following tracer administration. The unit contains a resuscitation trolley which contains equipment for use in the event of a clinical emergency, such as airway support and for vascular access. The equipment contained in the resuscitation trolley is compliant with UK Resuscitation Council recommendations. At a minimum, all clinical members of the research team, in addition to PET/CT clinical staff members, are trained in providing basic life support. Therefore, they will be suitably qualified to use the available resuscitation equipment. A clinical member of the research team will also be present during and following tracer administration. The unit is fully supported by CUH's rapid response team in the unlikely event of an acute deterioration following [¹⁸F]CETO administration. Any participant who experiences a SAR will not receive any further doses of [¹⁸F]CETO.

Similarly, the CLRF is embedded within the main hospital and is fully supported by the CUH clinical teams should a participant require urgent/high dependency care.

15 Evaluation of Results (Definitions and response/evaluation of outcome measures)

The study is primarily a safety study. Although adrenal uptake of [¹⁸F]CETO will be assessed as a secondary objective, the study is not powered to allow statistical analysis of the findings.

List-mode PET data acquisition during the dynamic scanning phase will enable retrieval of static images at any point for the duration of the PET-CT scan. Analysis of static images across different timepoints will allow us to determine when adrenal background uptake is most favourable and, in patients with primary aldosteronism, when the signal (tumour) to background (normal adrenal uptake) is maximally separated. Assessment of adrenal uptake of [18F]CETO will be undertaken by two nuclear medicine physicians.

Confirmation of adrenal uptake will be assessed in the first 4 participants to ensure that the study can continue. This will necessarily be performed in a non-blinded manner and will depend on a joint assessment by a nuclear medicine physician and the PI. In contrast, all SUV measurements performed as part of the secondary outcome measures will be determined at the end of the study by two nuclear medicine physicians who will independently assess each study in a fully blinded manner [i.e. with no knowledge of participant status (healthy volunteer versus patient) nor the date/timing of the scan – all scans will be fully anonymised].

We will be comparing the adrenal uptake (as measured by SUV_{max} over the adrenal gland) between healthy volunteers and patients on [¹⁸F]CETO PET-CT. In detail, a region of interest (ROI) will be drawn over the adrenal glands on each axial slice of the co-registered PET-CT scan, and the maximum standardised uptake value (SUV_{max}) recorded. The SUV_{max} is a better indicator of true uptake in small lesions when compared to mean SUV due to partial volume affects caused by the limited spatial resolution. Each participant will have SUV_{max} generated at 3 timepoints over the 90 minute duration of the dynamic PET-CT. In patients, there will be a comparison of the SUV_{max} between the adrenal glands, to determine the ability of [¹⁸F]CETO distinguish between unilateral and bilateral adrenal disease.

Additional data, including formal pharmacokinetic studies, will be obtained in a parallel study undertaken by our trial collaborators in Uppsala, Sweden.

16 Statistics

16.1 Statistical methods

The trial has not been undertaken with a power calculation as the primary objective is to assess the safety and tolerability of [18F]CETO and not to evaluate tracer efficacy. Summary statistics of safety data will be prepared for review and evaluation by the independent DMC

16.2 Interim analyses

Due to the short duration of the trial, no interim analysis is planned. Safety signals will be actively monitored by the independent DMC.

16.3 Number of Participants to be enrolled

Up to 11 participants will be recruited consisting of up to 5 healthy volunteers and 6 patients with a diagnosis of PA. The recruitment of 5 healthy volunteers is a sufficient number to evaluate the safety and tolerability of a single [¹⁸F]CETO administration. The recruitment of up to 6 PA patients will provide additional safety data and also provide preliminary information regarding [¹⁸F]CETO uptake in normal and abnormal adrenal tissue.

16.4 Criteria for the premature termination of the trial

The safety data and PET-CT data will be reviewed by the DMC following injections of [18F]CETO in the first 3 participants to provide an initial evaluation of [18F]CETO safety, and confirm the trial is able to proceed.

Furthermore, automatic trial stopping criteria will be met if a single participant experiences any serious adverse reaction (SAR, i.e. a serious adverse event considered at least possibly related to the IMP administration). Stopping criteria will additionally apply if any severe non-serious adverse reactions (ARs) develop in two participants, independent of whether or not these are within the same system-organ-class. The following will then occur:

- The trial will be halted via a substantial amendment to the MHRA.
- No further dosing or recruitment will be undertaken
- A safety review by the DMC will be conducted to determine how to proceed with the trial
- Any patients who have their dosing discontinued as a result of a SAR or a severe nonserious AR will be withdrawn from the trial
- Re-initiation of the trial can only be considered after MHRA approval via a substantial amendment. Any concurrently active participants will be re-consented before further IMP doses are administered, and all completed participants will be informed of the SAR or severe non-serious ARs.

Finally, if there is no demonstrable [¹⁸F]CETO uptake into human adrenal tissue in the first 4 participants (either healthy volunteers and/or patients), the trial will be halted and the DMC will be asked to consider if the trial should be stopped.

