Results from metabolite analyses of venous blood samples from *Macaca fascicularis* show [¹⁸F]CETO has a bi-phasic metabolism with a fast first phase with an approximate plasma half-life of 10 minutes followed by a second slower phase. At the end of a typical dynamic PET-scan of 90 minutes [¹⁸F]CETO represents about 10% of radioactivity in plasma. The kinetics of metabolism are compatible with the kinetics of tissue uptake, and [¹⁸F]CETO shows sufficient stability to give high uptake in the adrenals as well as elimination of the tracer from blood.

Pharmacology Studies - Rats

Toxicology assessment for [¹⁸F]CETO, based on the micro-dosing guidelines, was performed in rats, using 1000-fold and 100-fold the expected human dose of 10 micrograms/per subject (details provided in the investigator brochure and Appendix 1). Administration of [¹⁸F]CETO by a single intravenous injection was well tolerated in male and female rats at dose levels of 0.0143 and 0.143 mg/kg. Based on these outcomes, we consider [¹⁸F]CETO has appropriate properties for phase 1 human PET studies.

As anticipated at these high doses of 0.143mg/kg (1000-fold dosing), [¹⁸F]CETO suppressed plasma corticosterone levels in keeping with its known pharmacological properties. While this is unlikely to be relevant to human studies with [¹⁸F]CETO given the much lower dose that will be administered, we will undertake an assessment of adrenal function 24 hours after [¹⁸F]CETO administration to confirm this is not a clinically relevant concern.

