9.6 Trial Outcome Measures

9.6.1 Primary outcome Measure

• The primary outcome measure is the overall safety of [¹⁸F]CETO. This will be assessed according to the frequency of adverse events, serious adverse events, clinically significant changes in vital signs, ECG and laboratory parameters.

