10.2 Exclusion Criteria

All participants:

- allergy to radiographic contrast agents
- allergy or contraindication to synacthen
- pregnancy, breastfeeding, or the intention to become pregnant during the 6 months following trial participation
- positive pregnancy test at the screening or baseline visits
- assessed by the investigator as being unable or unwilling to comply with the requirements of the study protocol.
- receipt of another IMP as part of a CTIMP
- prior radiation exposure as part of previous research studies
- recreational drug use, or substance/alcohol dependency
- clinically abnormal screening blood tests [including abnormal short synacthen test (SST)].

Additional exclusion criteria for **healthy volunteers**:

- women of child-bearing potential (i.e. fertile, following menarche and until becoming post-menopausal unless permanently sterile. Permanent sterilisation methods include hysterectomy, bilateral salpingectomy and bilateral oophorectomy)
- exposure to radiation during their work
- received more than 10 mSv of radioactivity in the past 12 months
- any subject with a history of adrenal disease or who, at the screening visit, reports symptoms, or exhibits physical signs, that could be consistent with previously unsuspected adrenal disease

Additional exclusion criteria for **patients**:

• allergy or contraindication to dexamethasone treatment (or lactose intolerant)

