The following morning, participants will have repeat blood tests including a short synacthen test (SST) to evaluate adrenal function. Although the doses of [18F]CETO administered in humans will be significantly lower than used in the rat microdosing studies, and it is therefore very unlikely that clinically relevant short-term adrenal suppression will occur, we have included a SST following injection of the radiotracer to provide reassurance that adrenal function remains normal in participants. Following review of the results by a clinical member of the research team, participants will be discharged from the CLRF. In the unlikely event that a participant returns an abnormal SST result, they will be reviewed by a member of the clinical research team and the decision will be taken as to whether they temporarily need low dose hydrocortisone treatment until the test is repeated one week later.

Dexamethasone Prescription (Patients only)

Prior to discharge from the CLRF and where SST results were confirmed to be acceptable, patients will be provided with a prescription for dexamethasone 500 micrograms four times daily for three days (total 12 doses). Dexamethasone will be self-administered for three days (total 12 doses) prior to the repeat PET-CT scan. Patients will be provided with contact details for the research team if they have any questions while taking dexamethasone. The purpose of this pre-treatment with dexamethasone will be to improve the ability to distinguish between abnormal and normal adrenal tissue in the subsequent scan. Therefore, a second scan with dexamethasone pre-treatment will only be required for patients and not healthy volunteers.

Follow up visit for those with abnormal synacthen test result

Any individuals with an abnormal SST approximately 24 hours post injection of [18F]CETO will be invited to a follow-up visit at 7 (+/-2 days) for a repeat test. At that visit, the participant will also be assessed by a clinical member of the research team. A repeat SST will be conducted during this visit, and the results assessed by the clinical research fellow and, if clinically indicated (for example if a further abnormal result is returned), by the Principal Investigator before the participant goes home.

In the extremely unlikely event that the abnormality persists, the participant will continue to be monitored within the trial until one of the following conditions is met:

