A Single Dose Study of pCI-Fluoroetomidate by Intravenous Injection in Wistar Rats with a 14-Day Recovery Period (Summary)

The objective of this study was to determine the potential toxicity of pCI-Fluoroetomidate, when given intravenously as a single dose to Wistar rats and to evaluate the potential reversibility of any findings.

The study design was as follows:

Text Table 1 - Experimental Design

	No. of Animals					
	Main			Dose	Dose	Dose
Group No.	(Recovery) Male Female		Test Material	Level (mg/kg)	Concentration (mg/mL)	Volume (mL/kg)
1	10 (5)	10 (5)	Vehicle	(mg/kg)	0	1 1
2	10 (5)	10 (5)	Test Item	0.0143	0.0143	1
3	10	10	Test Item	0.143	0.143	1
4 ^a	-	3	Test Item	0.143	0.143	1

^a Group was only used for Corticosterone determination.

The following parameters and end points were evaluated in this study:

- clinical signs
- body weights
- food consumption
- clinical pathology parameters (hematology, coagulation, and clinical chemistry), corticosterone determination (non-GLP),
- gross necropsy findings
- organ weights
- and histopathologic examinations.

No mortality occurred during the study. There were no test item-related clinical signs or effects on body weight, food consumption, clinical pathology and organ weights or any macro- and microscopic alterations observed in males and females up to 0.143 mg/kg.

A clear decrease in corticosterone levels were seen in all three females at 24 hours postdose when compared to predose.

In conclusion, administration of pCI-Fluoroetomidate by a single intravenous injection was well tolerated in male and female rats at dose levels of 0.0143 and 0.143 mg/kg.

Further details regarding the study can be obtained from the CETO trial team. Please quote the CETO Toxicology-Charles River report, 'A Single Dose Study of pCI-Fluoroetomidate by Intravenous Injection in Wistar Rats with a 14-Day Recovery Period', Test facility study number 20158118.

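### The automatic safety halts cannot count an asymptomatic, non-serious abnormal 24-hour short synacthen test (SST), although the SST was added to detect adrenal suppression; the gap is narrow and cheap to close

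*Protocol*

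**What the plan says.** **The halts.** Sections 12.5 (Ongoing Safety Review) and 16.4 give two automatic safety halts. One is a single serious adverse reaction (SAR) in one participant. The other reads: "Stopping criteria will additionally apply if any severe non-serious adverse reactions (ARs) develop in two participants". Either stops dosing and recruitment, and restarting needs MHRA approval of a substantial amendment. Section 16.4 adds a separate trigger: if the first 4 participants show no adrenal uptake, the trial is halted and the question goes to the DMC.

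**Severity.** Section 13.4.3 defines severe as "Significant impairment of functioning; the subject is unable to carry out usual" activities, and/or a risk to life. It has no laboratory grade. Even mild presumes that the participant notices the event.

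**The SST.** Section 7.2 reports that the compound, at 1000 times the human dose in rats, "suppressed plasma corticosterone levels in keeping with its known pharmacological properties". The Appendix says: "A clear decrease in corticosterone levels were seen in all three females at 24 hours postdose when compared to predose". Section 12.5 gives the purpose of the human test: "we have included a SST following injection of the radiotracer to provide reassurance that adrenal function remains normal in participants". Section 10.2 excludes anyone with an abnormal screening SST.

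**What follows an abnormal SST.** Under 12.5 the participant has a clinical review, a decision on hydrocortisone and a repeat test at 7 (±2) days. A patient with an abnormal result has no second scan.

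**Trial-level oversight.** The primary outcome in 9.6.1 includes "clinically significant changes in vital signs, ECG and laboratory parameters". The DMC receives safety summaries (16.1), monitors safety signals (16.2) and must review the data after the first 3 participants before the trial continues (16.4).

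**The concern.** The halt rule and the safety test do not connect. Adrenal suppression is the only test-item effect that the protocol reports from the rat study, and it is measured by a laboratory test. The two-participant halt counts only events graded by symptoms and function. Suppression seen on the SST but not felt by the participant therefore falls outside the rule.

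After the DMC review at 3 participants, the protocol gives no date, count or trigger that links repeated asymptomatic abnormal SSTs to a decision about dosing new people. A pause would depend on an investigator classing a result as serious, or on the DMC acting under general monitoring. At stake is whether later participants in a first-in-human trial are dosed before anyone is required to consider a recurring, foreseen effect.

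**Working it through.** **Step 1: definitions side by side.** Take a participant with a normal screening SST (10.2) and an abnormal SST the morning after dosing, without symptoms and judged not serious.

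- It can be an adverse event: 13.1.1 covers abnormal laboratory findings.
- It can be an adverse reaction: 13.4.2 treats a possible causal link as drug-related.
- It does not meet the SAR halt, because it is not serious (13.1.4).
- It does not meet the severe halt, because function is intact and life is not at risk (13.4.3).

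Such results therefore contribute zero to either halt, however many there are. This follows from the text and needs no calculation.

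**Step 2: how often the gap could matter.** The protocol states no SST event rate and no operating characteristic for the halts, so there is no figure of its own to reproduce. Inputs: 11 participants (16.3); DMC review after 3 (16.4), leaving 11 − 3 = 8. Assumptions: independent participants with a common probability p of an asymptomatic, non-serious abnormal result.

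The exposed path is a clean DMC review followed by repeated abnormal results:

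P(0 of 3, then at least 2 of 8) = (1−p)³ × [1 − (1−p)⁸ − 8p(1−p)⁷]

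- p = 1%: 0.9703 × 0.0027 = 0.003
- p = 5%: 0.8574 × 0.0572 = 0.049
- p = 10%: 0.7290 × 0.1869 = 0.136

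The chance that the DMC review already contains at least one such result is 1 − (1−p)³.

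| Assumed p | At least 1 in first 3 | None in first 3, then at least 2 of 8 |
|---|---|---|
| 1% | 0.03 | 0.003 |
| 5% | 0.14 | 0.05 |
| 10% | 0.27 | 0.14 |
| 20% | 0.49 | 0.25 |
| 30% | 0.66 | 0.26 |
| 50% | 0.88 | 0.12 |

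The last column is an upper bound on the gap, because it gives no credit to DMC action between participants 4 and 11.

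**Step 3: false alarms from a two-participant hold.** Suppose all abnormal results are chance findings and each is judged possibly related.

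- At least one DMC referral: 1 − (1−p)¹¹ = 0.105 at p = 1%, 0.431 at p = 5%.
- A hold: 1 − (1−p)¹¹ − 11p(1−p)¹⁰ = 0.005 at p = 1%, 0.102 at p = 5%.

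**The case against.** The case for leaving the rule alone is substantial.

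- **Early detection.** Under 12.5 the first participant goes through the trial alone, including the next-day SST, before anyone else is dosed. There is no dose escalation (11.1.1.6), so a strong effect should appear early. At a true rate of 50%, the review at 3 participants would contain an abnormal SST with probability 0.88.
- **Dose margin.** Suppression was reported at 1000 times the 10 microgram cap. The expected dose is 0.2 to 2 micrograms (section 8), so the margin is 5,000- to 50,000-fold. Section 12.5 calls clinically relevant suppression very unlikely, and nothing in the protocol supports rates of 5% or 10%.
- **Important cases are covered.** A result that needs hydrocortisone may be an important medical event (13.1.4), hence a SAR that halts the trial at one case. Affected patients get no second dose, and volunteers have only one.
- **Design choice.** Halting on seriousness or severity is a legitimate choice, and DMC triggers may sit in a charter that is not shown.

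These points stand and limit the weight of the finding. They also rule out a stronger reading that a reader might infer: that suppression in all 11 participants could pass without review. Both automatic halts would indeed stay unmet, but the sentinel and the first 3 participants would all be abnormal, and the DMC must confirm that the trial can go on. Nor do SST results escape oversight, since they can be adverse events, belong to the primary outcome and reach the DMC.

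What the objection does not remove is the mismatch in the rule itself. The protocol already treats any abnormal post-dose SST, with or without symptoms, as enough to deny that patient a second dose, yet no number of them holds dosing of new participants. Section 16.4 also shows that a trigger not based on symptoms fits this design, because absent uptake has a count and a DMC referral.

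**Conclusion.** The point holds in a limited form. By the protocol's own definitions, asymptomatic, non-serious abnormal 24-hour SSTs cannot count toward either automatic safety halt. The practical gap mainly concerns participants 4 to 11 when the true rate is low enough for the first 3 to be clean. Its size is at most 0.003, 0.05 and 0.14 at assumed rates of 1%, 5% and 10%. It would be about 0.25 at 20% to 30%, but the protocol gives even less reason to expect such rates. All these figures rest on assumed rates, independence and full recruitment of 11; only the logical exclusion is fixed by the text.

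This is a weakness in a stated stopping rule, not an error that endangers the trial. It is worth correcting because the remedy costs little and uses a test that is already done.

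**What to change.** In 12.5 and 16.4, with the synopsis aligned, add a third safety trigger:

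- Any abnormal post-dose SST at least possibly related to the IMP is reported promptly to the DMC.
- When two participants have such a result, further dosing is held for DMC review, whatever the symptoms or severity grade.
- The hold follows the pattern of the uptake trigger in 16.4 (hold and DMC referral). State that it does not by itself invoke the MHRA substantial-amendment restart, which stays with the SAR and severe-reaction halts.

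Those two halts are unchanged, and no new clinical threshold for an abnormal SST is proposed.

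**Cost.** No new procedure is needed, since every participant already has an SST after the first dose. The price is an occasional unnecessary DMC referral (10% at a 1% chance-abnormal rate, 43% at 5%) or hold (0.5% and 10%). Requiring a normal SST at entry should keep chance abnormalities toward the low end.

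**Limit.** The number of participants spared depends on reading each SST before the next person is dosed. Section 11.1.1.8 allows several participants on one day, so the benefit is smaller if dosing is grouped.
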